- e. Subjects who completed the 6-month post-prime visit (which has been replaced with the 6-month post-boost visit per protocol Amendment 2) prior to approval of Amendment 2 were required to also attend the 6-month post-boost visit after approval of Amendment 2.
- f. Signing of the informed consent form (ICF) and/or assent needs to be done before the first study-related activity. After reading but before signing the ICF/assent, the TOU will be administered.
- g. The investigators should ensure that all study enrollment criteria have been met at the end of the screening phase. Minimum criteria for the availability of documentation supporting the eligibility criteria are described in Section [17.4](#).
- h. Prestudy therapies up to 30 days prior to the start of screening and previous vaccinia/smallpox vaccination at any time prior to study entry must be recorded in the case report form (CRF). HIV-therapy should be recorded for HIV-infected subjects.
- i. Only for women of childbearing potential.
- j. Only for women >45 years of age with amenorrhea for less than 2 years or ≤45 years of age with amenorrhea for more than 6 months.
- k. If a subject's clinical status changes (including available laboratory results or the receipt of additional medical records) after screening so the subject no longer meets the eligibility criteria, the subject should be excluded from further participation in the study.
- l. After the prime and boost vaccinations, subjects will remain at the site for a total of 60 ( $\pm 15$ ) minutes post-vaccination to monitor for the development of any acute reactions, or longer if deemed necessary by the investigator. Solicited and unsolicited adverse events emerging during the observation period at the site will be recorded in the CRF.
- m. Prior to study vaccine administration.
- n. A single, 12-lead ECG (supine) after 5 minutes of rest will be performed for subjects  $\geq 18$  years of age (Cohorts 1 and 2a) at screening and interpreted locally. Additional ECG monitoring may be performed at other time points during the study if clinically indicated. If blood sampling or vital sign measurements are scheduled at the same time point as the ECG recording, the procedures should preferably be performed in the following order: vital signs, ECG, blood draw.

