**Table 3: Visit Windows**

Visit Description	Day	Window
Seven Days Post-prime Vaccination	Day 8 for all groups	±2 days
Fourteen Days Post-prime Vaccination (only in Groups 2 and 3 from Cohort 1)	Day 15 for Group 2 and Group 3	±2 days
Boost Vaccination	Day 29 for Group 1 Day 57 for Group 2 Day 85 for Group 3	±3 days
Seven Days Post-boost Vaccination	Day 36 for Group 1 Day 64 for Group 2 Day 92 for Group 3	±2 days
Twenty-one Days Post-boost Vaccination	Day 50 for Group 1 Day 78 for Group 2 Day 106 for Group 3	±3 days
Forty-two Days Post-boost Vaccination	Day 71 for Group 1 Day 99 for Group 2 Day 127 for Group 3	±3 days
Follow-up 6 Months Post-boost a	Day 209 for Group 1 Day 237 for Group 2 Day 265 for Group 3	±15 days
Follow-up 1 Year Post-prime	Day 365 for all groups	±30 days

Refer to [Table 6](#) (Section 9.1.7) for the visit windows that will be allowed for the Cohort 1 substudy.

a Subjects who completed the 6-month post-prime visit (which has been replaced with the 6-month post-boost visit per protocol Amendment 2) prior to approval of Amendment 2 were required to also attend the 6-month post-boost visit after approval of Amendment 2.

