**Table 5: Visit Windows for Subjects Who are Not Willing or Not Allowed to Receive the Late Boost Vaccination**

Visit Description a	Day	Window
Seven Days Post-prime Vaccination	Day 8 for all groups	±2 days
Fourteen Days Post-prime Vaccination (only in Groups 2 and 3 from Cohort 1)	Day 15 for Group 2 and Group 3	±2 days
Three Months Post-prime Vaccination b	Day 90 for all groups	±30 days
Six Months Post-prime Vaccination	Day 180 for all groups	±30 days
Nine Months Post-prime Vaccination b	Day 270 for all groups	±30 days
One Year Post-prime vaccination	Day 365 for all groups	±30 days

a Subjects will be asked to return to the site approximately every 3 months after the prime vaccination for safety assessments, until the 1-year post-prime follow-up visit (note: the 3-month and 9-month post-prime visits may be conducted by best local practice, see footnote b). In case the subject is unable to return for these visits, this will not constitute a major protocol deviation and subjects will be considered lost to follow-up.

b The 3-month and 9-month post-prime visits may be conducted by best local practice: either by telephone contact, site visit or home visit.

Adverse events, whether serious or non-serious, will be collected at all visits from signing of the ICF onwards until 42 days after the last vaccination (ie, Day 42 post-prime vaccination for subjects who did not receive a boost vaccination). Thereafter, reporting will be limited to all serious adverse events and IREs up to the subject's last study-related procedure. Solicited local and systemic adverse events (reactogenicity, see below) will be reported by the subject until 7 days after each administration of study vaccine. Adverse events will be followed by the investigator as specified in Section 12. Subjects will be instructed to contact the investigator before the next visit (ie, 6 months post-boost visit, or 3 months post-prime visit for subjects who are not willing or not allowed to receive a late boost vaccination) if they experience any adverse event or intercurrent illness that they perceive as relevant and/or can be possibly related to study vaccine in their opinion.

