2.1. Analysis Visit Windows and Periods

Because subjects do not always adhere to the protocol visit schedule, the following rules will be applied to assign actual visits (immunogenicity assessments) to analysis visits. The analysis visit windows and target days for each visit are displayed in

[Table 1](#). The reference day will be defined as:

- Day of first (Dose 1) vaccination if the actual visit occurs prior to the second (Dose 2) vaccination.
- Day of second (Dose 2) vaccination if the actual visit occurs after the second vaccination but prior to the third (Dose 3: only for subjects in the substudy) vaccination.

- Day of third (Dose 3: only for subjects in the substudy) vaccination if the actual visit occurs after the third vaccination.

Only the analysis time points and assays that are in scope for a specific statistical analysis (e.g. Interim Analysis, Final Analysis) are to be considered when assigning assessments to analysis visit windows. If a subject has 2 or more assessments within the same interval (analysis visit window), the one closest to the target day will be used for generating tables with descriptive statistics and graphical displays presenting data per time point. If 2 assessments are equidistant from the target day within the same interval, the latest assessment will be used. All assignments will be made in chronological order.

Because the analysis of adverse events (AEs) and laboratory abnormalities (except CD4+ cell counts in HIV-infected subjects) will be presented per period (and not per time point), these will be assigned to the analysis period and/or phase based on [Table 2](#). For CD4+ cell counts, the electronic case report form (eCRF) visit schedules will be used for the post baseline assessments. If only unscheduled visits are present for a time point, then the one closest to the scheduled visit will be used. If distances of multiple assessments to the scheduled visit are equal, the measurement with the latest date will be used. Similar to the CD4+ cell counts, the eCRF visits will also be used to present vital signs data of Cohort 3 subjects per time point.

Table 1: Analysis Visit Windows

Time Interval (Label on Output)	Time Interval PP ^a (Day)	Time Interval IG ^b (Day)	Target Time Point (Day)
Prior to Second (Dose 2) Vaccination			
Day 1 (Baseline)	≤ 1	≤ 1	1
Day 15 (14 days Post-dose 1)	[13; 17]	[2; 21]	15
Day 29 (28 days Post-dose 1)	[26; 32]	[22; 42]	29
Day 57 (56 days Post-dose 1)	[54; 60]	[43; 70]	57

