Day 85 (84 days Post-dose 1)	[82; 88]	[71; 98]	85
Day 141 (140 days Post-dose 1)	NA	[99; 168]	-
Day 197 (196 days Post-dose 1)	NA	[169; 224]	-
Day 253 (252 days Post-dose 1)	NA	[225; 280]	-
≥Day 281 (≥280 days Post-dose 1) ^d	NA	≥281	-
Day 365 (364 days Post-dose 1)	[335; 395]	≥281	365
After Second (Dose 2) Vaccination but Prior to Third (Dose 3) Vaccination			
Day 36 (7 days Post-dose 2)	[6; 10]	[2; 15]	8
Day 64 (7 days Post-dose 2)			
Day 92 (7 days Post-dose 2)			
Day 148 (7 days Post-dose 2)	NA	[16; 101]	22
Day 204 (7 days Post-dose 2)			
Day 260 (7 days Post-dose 2)			
≥Day 289 (7 days Post-dose 2)			
Day 50 (21 days Post-dose 2)	[19; 25]		

Time Interval (Label on Output)	Time Interval PP ^a (Day)	Time Interval IG ^b (Day)	Target Time Point (Day)
Day 78 (21 days Post-dose 2)	NA		
Day 106 (21 days Post-dose 2)			
Day 162 (21 days Post-dose 2)			
Day 218 (21 days Post-dose 2)			
Day 274 (21 days Post-dose 2)			
≥Day 303 (21 days Post-dose 2)			
Day 209 (180 days Post-dose 2)	[166; 196]	[102; 196]	181
Day 237 (180 days Post-dose 2)			
Day 265 (180 days Post-dose 2)			
Day 321 (180 days Post-dose 2)	NA		
Day 377 (180 days Post-dose 2)			
Day 433 (180 days Post-dose 2)			
≥Day 462 (180 days Post-dose 2)			
Day 365 (364 days Post-dose 1) ^c	[335; 395]	≥222	365
Day 365 (Pre-dose 3) ^f	[335; 395]	≥365	-
After Third (Dose 3) Vaccination			
Day 369 (4 days Post-dose 3)	[4; 6]	[2; 6]	5
Day 372 (7 days Post-dose 3)	[6; 10]	[7; 15]	8
Day 386 (21 days Post-dose 3)	[19; 25]	[16; 101]	22
Day 545 (180 days Post-dose 3)	[166; 196]	[102; 273]	181
Day 730 (365 days Post-dose 3)	[335; 395]	≥274	365

^a The analysis based on the per protocol (PP) analysis set will be restricted to data points that fall within this window (ie, protocol-defined window).

^b The analysis based on the immunogenicity (IG) analysis set will be restricted to data points that fall within this window.

^c This analysis visit (Day 15) applies only to subjects in Groups 2 and 3 of Cohort 1.

^d This analysis visit is only applicable to the sensitivity analysis of subjects in Group G (ie, ≥281-day interval vaccination schedule) as shown in [Table 3](#) below. For the other analyses (ie, non-sensitivity), this will correspond to the Day 365 analysis visit.

^e For the windows after Dose 2 administration, only Day 365 (364 days Post-dose 1) window is taken with respect to the day of Dose 1 administration.

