^f This analysis visit applies only to the subjects in the substudy (ie, Groups 1 and 2 subjects in Cohort 1 who received 3rd vaccination). For this visit, the assessment closest (but prior) to the vaccination should be used. If this visit coincides with the Day 365 (Day 365 Post-dose 1) visit, then the assessment should be assigned to both visits.

NA: Not applicable.

Note 1: The analysis windows and target days are based on the relative day (ie, with respect to the reference day [day of Dose 1, Dose 2 or Dose 3 administration]). The counting restarts from the day of a vaccination (ie, clock reset).

Note 2: Derivation of changes from pre-dose should be performed with respect to the reference value.

Time Interval (Label on Output)	Time Interval PP ^a (Day)	Time Interval IG ^b (Day)	Target Time Point (Day)
------------------------------------	--	--	----------------------------

Note 3: Immunogenicity sample collection at Day 141, Day 197, Day 253 and Day 281 visits were not planned according to the protocol. However, these visits were recorded for some Cohort 1 subjects due to the study pause (ie, late second [Dose 2] vaccination). If the analysis visit window contains the day of actual boost vaccination for these visits, then the assessment closest to the vaccination will be used.

Note 4: The same (ie, with respect to the number days since boost vaccination) post-boost visits are labeled differently. Day 36, Day 50 and Day 209 apply only to the 28-day interval schedule, Day 64, Day 78 and Day 237 apply to the 56-day interval schedule. Day 92, Day 106 and Day 265 apply only to the 84-day interval schedule. Day 148, Day 162 and Day 321 apply only to the 140-day interval schedule. Day 204, Day 218 and Day 377 apply only to the 196-day interval schedule. Day 260, Day 274 and Day 433 apply only to the 252-day interval schedule. \geq Day 289, \geq Day 303 and \geq Day 462 apply only to the \geq 281-day interval schedule.

Note 5: All assignments will be made in chronological order. Once an assessment is assigned to an analysis window, it will no longer be used for a later window.

Table 2: Analysis Periods

Phase	Period	Interval	
		From	To
Screening		00:00 on the date of signing the informed consent form	One minute prior to Dose 1 administration on Day 1

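### The immunogenicity-set window for 180 days post-dose 2 closes at the per protocol limit, so 6-month samples 16 or more days late are labelled Day 365 or left out of the tables

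*SAP*

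**What the plan says.** SAP Section 2.1, Table 1, sets two windows per visit, one for the per protocol set and one for the IG set. Those that matter here are:

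| Row | Per protocol | IG | Target |
|---|---|---|---|
| 21 days post-dose 2 | [19; 25] | [16; 101] | 22 |
| 180 days post-dose 2 | [166; 196] | [102; 196] | 181 |
| Day 365, after Dose 2 | [335; 395] | ≥222 | 365 |
| 180 days post-dose 3 | [166; 196] | [102; 273] | 181 |
| Day 365, before any Dose 2 | [335; 395] | ≥281 | 365 |

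On the IG column the footnote says: "The analysis based on the immunogenicity (IG) analysis set will be restricted to data points that fall within this window". Days are counted from the most recent dose, with one exception after Dose 2: "only Day 365 (364 days Post-dose 1) window is taken with respect to the day of Dose 1 administration". If several samples share a window, "the one closest to the target day will be used for generating tables with descriptive statistics and graphical displays presenting data per time point". Assignment is chronological: "Once an assessment is assigned to an analysis window, it will no longer be used for a later window".

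Protocol Table 3 schedules the 6-month post-boost visit at "Day 209 for Group 1 Day 237 for Group 2 Day 265 for Group 3", each ±15 days. Subjects who had already completed the former 6-month post-prime visit "were required to also attend the 6-month post-boost visit after approval of Amendment 2" (Time and Events Schedule). SAP Section 2.3 makes the per protocol set primary for immunogenicity and repeats the analysis on the IG set. Protocol Section 11.6 plans to describe differences between schedules at 21 days post-boost, 6 months post-boost and Day 365.

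**The concern.** The IG repeat exists to show what happens when the per protocol restrictions are relaxed. At 6 months after the boost it relaxes timing on the early side only. A subject who attends 16 days late has a usable 6-month measurement that is far nearer to 6 months than to 1 year, yet the stated rules assign it to Day 365.

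There it does one of two things. If the subject has no sample nearer Day 365, a sample taken 6 to 7 months after the boost becomes the 1-year value. If there is such a sample, the late one is tabulated nowhere.

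Off-schedule samples are foreseeable. Amendment 2 recalled some subjects for an additional visit, and serum is to be drawn at early withdrawal. A subject who withdraws has no later Day 365 sample, which is the case in which relabelling occurs. The distance of the relabelled sample from Day 365 differs by schedule, and schedules are what these summaries describe.

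**Working it through.** **Conversion.** Study day = boost day + relative day − 1, with on-time boosts on Day 29, 57 and 85.

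**Reproducing the plan's limits.**
- IG lower limit: midpoint of targets 22 and 181 = 101.5, so 102. It agrees.
- IG upper limit: 181 + 15 = 196, the per protocol limit. It agrees, but it is not a midpoint.
- After Dose 3: (181 + 365)/2 = 273, the midpoint. It agrees.
- Day 365 lower limit: the earliest in-window Group 1 boost is Day 26. The first day past relative Day 196 is then 26 + 197 − 1 = 222. It agrees, so there is no gap between the two windows when boosts are in window.

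**Where the present limits fall.**

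| | Group 1 (28-day) | Group 2 (56-day) | Group 3 (84-day) |
|---|---|---|---|
| 6-month target, study day | 209 | 237 | 265 |
| Last study day of IG window (boost day + 195) | 224 | 252 | 280 |
| First day assigned to Day 365 | 225 | 253 | 281 |
| Days before Day 365 | 140 | 112 | 84 |
| Midpoint of 6-month target and Day 365 | 287 | 301 | 315 |
| Lateness at that midpoint (days) | 78 | 64 | 50 |
| Midpoint as relative day | 259 | 245 | 231 |

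Tolerance is 196 − 181 = 15 days on the late side and 181 − 102 = 79 days on the early side.

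**Example: a 6-month sample 20 days late (relative Day 201).** It falls on study Day 229, 257 or 285, past the 180-day window and inside Day 365 (≥222). If the subject also has a Day 365 sample, that one is nearer the target and the late sample is not tabulated. If not, the late sample is reported as Day 365, which is 136, 108 or 80 days early.

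**Former 6-month post-prime visit.** Its day is taken from Protocol Table 5, "Day 180 for all groups", which applies to subjects without a boost. Using it for boosted subjects is an assumption. The relative day would be 180 − 29 + 1 = 152, 180 − 57 + 1 = 124 and 180 − 85 + 1 = 96. The first two lie in the 180-day IG window. The third lies in the 21-day IG window [16; 101].

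**The case against.** **The Dose 3 comparison is not exact.** After Dose 3, both later visits run on one clock and share one midpoint. After Dose 2, Day 365 runs on the Dose 1 clock, so the midpoint differs by schedule. This stands, and it counts against simply copying the midpoint rule: limits of 259, 245 and 231 would allow 78, 64 and 50 days of lateness and so build a schedule difference into the 6-month value. The rule also breaks down for long intervals. At 196 days the 6-month visit is Day 377, after Day 365.

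**The SAP explains the window.** Its amendment history says the limits were updated so that per protocol data points are included. That explains an upper limit of at least 196, but not one of exactly 196.

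**The consequence is small.** The primary immunogenicity analysis uses [166; 196] and [335; 395]. The secondary endpoint is ELISA at 21 days post-boost, no hypothesis is tested, and unused samples still appear in the listing. All of this stands.

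**Stronger readings that the documents do not support.**
- A reader might infer that the 79-day early reach is itself an error. It is the ordinary midpoint and is the same after Dose 3.
- A reader might infer that samples from 4 to 5 months after the boost do stand in for 6 months, and in Groups 1 and 2 only. That would need serum drawn from boosted subjects at the former visit, which is not documented, and no sample nearer Day 181 in the window. Nor is Group 3 exempt: a visit on study Day 186 is relative Day 186 − 85 + 1 = 102, inside the 180-day window.
- A reader might infer that the 21-day IG value in Group 3 is compromised. A relative Day 96 sample is used only if no sample nearer Day 22 exists.

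**Conclusion.** The point holds at low severity. Under the stated rules the IG repeat recovers no 6-month post-boost sample beyond the per protocol limit. It assigns such samples to Day 365, up to 140, 112 or 84 days before that target in Groups 1, 2 and 3. Whether a sample is then mislabelled or omitted depends on whether the subject has one nearer Day 365.

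This rests on on-time boosts and on reading the post-dose 2 limit of Day 222 as counted from Dose 1, which is how the footnote describes that row. The recall visit is documented; how late those visits fell is not. No count of affected subjects is given, so no bias in the schedule comparison can be sized, and the documents do not support a claim that the comparison is biased. The effect is confined to the IG repeat of exploratory time points, plus the 21-day IG value in Group 3 under the conditions above.

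**What to change.** Change SAP Table 1 for the 28-, 56- and 84-day schedules only:

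- Extend the IG window for 180 days post-dose 2 to [102; 231]. Relative Day 231 is the smallest of the three midpoints, so every schedule allows 231 − 181 = 50 days of lateness. With on-time boosts it closes on study Day 259, 287 and 315.
- Start the post-dose 2 Day 365 IG window at Day 316 on the Dose 1 clock. This still contains the per protocol window [335; 395].
- List samples between the two without assigning them to either visit: study Days 260–315 in Group 1 and 288–315 in Group 2, with no gap in Group 3 when the boost is on time.
- Leave the rows for intervals of 140 days and longer at their present limits, or give them their own. At 140 days the midpoint is only relative Day 203, and from 196 days the visit order reverses.
- If serum was drawn from boosted subjects at the former 6-month post-prime visit, show it under its own label and do not let it fill the 21-day or 180-day post-boost visit.

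The cost is edited limits and one label, with no new data. The downside is a somewhat wider timing spread in the 6-month IG summary and a few samples that are only listed. Subjects recalled after they had already completed Day 365 would return at about Day 335 or later, and this change would not recover their late 6-month samples.
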